
Overall Study Aim

The overall aim of this Phase II, proof of concept study is to evaluate the efficacy and safety of naloxegol (versus placebo) in preventing lower GI tract paralysis in critically ill adults initiated on scheduled intravenous (IV) opioid therapy.

2. 1 Primary objective

The primary objective of this single-center, Phase II, proof of concept study in critically ill adults initiated on scheduled IV opioid therapy is to compare the incidence of lower GI tract paralysis [from the time of a study enrollment (i.e., randomization) to ICU discharge, death or 10 days of study drug administration (whichever comes first)] between naloxegol 25mg daily and placebo-treated groups.

Drug Substance: Movantik
 Study Number: ESR-15-11000
 Tufts IRB #12043
 Version: Protocol version #19
 Date: September 10, 2018

Note:

1. For the purposes of the study, any rectal output will be considered a SBM as long as it is not temporally related to the insertion of a rectal tube or the insertion of a suppository (as per the study laxative protocol (Appendix 1)).
2. Patients with preexisting lower GI tract paralysis are excluded from the study.
3. Patients not expected to survive their ICU stay are excluded from the study.

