4. SUBJECT SELECTION CRITERIA

The investigators will maintain a screening log for the duration of the study.

Each patient will meet all of the inclusion criteria and none of the exclusion criteria. A study screening sheet will be completed by a member of the investigative staff and confirmed by a second member of the investigation staff before randomization will occur.

All patients consecutively admitted to the medical ICU service who are admitted to the MICU, CCU, SICU or NCCU at Tufts Medical Center will be screened on a daily basis (through review of the ICU admission note, available laboratory data, the medication administration record, and the patient flowsheet by one of the study investigators who will determine if the patient meets all inclusion and exclusion criteria for participation in the study).

When the patient is found to meet all inclusion and no exclusion criteria, and Drs. [name], [name] or [name] have reviewed and signed the screening form, and the patient's primary ICU attending has approved their enrollment, the subject/legally authorized representative will be approached (either in person or by phone (ie. invited to come to Tufts MC to discuss the study) during the periods of 7am to 7pm.

4. 1. Inclusion criteria

- a. Admitted to the medical ICU service.
- b. Age \geq 18 years.
- c. Expected by the medical ICU attending physician to require admission to the MICU service for \geq 48 hours.
- d. Intravenous opioid administration in the prior 24 hours of \geq 100 mcg fentanyl equivalents (including both scheduled and "as needed" therapy).

Drug Substance: Movantik
Study Number: ESR-15-11000
Tufts IRB #12043
Version: Protocol version #19
Date: September 10, 2018

e. No objections from the MICU or attending physician for enrollment.

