12.2 Methods of statistical analysis

Baseline characteristics of patients will be compared using standard univariate methods (chi-square test, t-test) to confirm the randomization was successful in achieving comparable groups. To test the primary outcome (incidence of lower GI tract paralysis), given that there may be censoring (i.e., subject may die or withdraw from study before developing lower GI tract paralysis), we will present Kaplan-Meier curves for the naloxegol and placebo groups for the time to first development of lower GI tract paralysis (≥ 3 days without a SBM after study randomization) during the ICU stay up to 10 days and compare the curves using a log-rank test. If all subjects complete the study (e.g., no deaths, no withdrawal or loss-to-follow-up for other reasons), then we will instead compare the proportion of patients that develop lower GI tract paralysis after study randomization during the ICU stay up to 10 days between the naloxegol and placebo groups using a chi-square test. The secondary outcome, time to first SBM will be estimated using a Kaplan Meier time to event analysis and compared between groups using a log-rank test. The secondary outcome of the number of ICU days without a SBM will be compared between the naloxegol and placebo groups using the Poisson regression for count data and adjusting for total number of days in the ICU (up to a maximum of 10) as an offset term in the Poisson model. The secondary outcome of the average daily opioid requirements will be compared between groups using either a student t-test or nonparametric Wilcoxon rank-sum test if the assumptions of the student t-test fail to be met. Length of mechanical ventilation and ICU stay will be reported as medians and interquartile ranges and will be compared using the Wilcoxon Rank Sum Test. For all statistical tests of hypotheses, a two-sided p-value of ≤ 0.05 will be considered as statistically significant. As this is a Phase II proof of concept study a p value of <0.10 may still be worth consideration for future study, however. All statistical analyses will be performed using SPSS 17.0. (SPSS, Chicago, IL) or other comparable commercially available statistical software.

[figure not shown]

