12.2.2 Determination of sample size

Drug Substance: Movantik
 Study Number: ESR-15-11000
 Tufts IRB #12043
 Version: Protocol version #19
 Date: September 10, 2018

For the power analysis, the 4-day estimates of failure to defecate (i.e., failure to have a SBM) from the Kaplan-Meier plot presented in the Guardiola et. al. paper [4] was used as the estimate of lower GI tract paralysis. The figure below shows that the estimate of the percent of patients who failed to defecate (1 minus plotted proportion with defecation) by day 4 was 40% in the Prophylaxis group (i.e., the intervention group) vs. 90% in the non-prophylaxis (Treatment) group (i.e., the control group) (see yellow highlights in figure). We believe the 4-day estimate will be strongly related to the primary outcome of lower GI tract paralysis (≥ 3 days without a SBM).

4 estimated freedom of event (defecation) rates are 90% (Placebo) vs. 40% (Prophylactic treatment), all subjects have complete follow-up, and the analysis is done using the log-rank test to compare survival curves. As sensitivity analysis, the table also shows the power of the study with this sample size under different scenarios. Because this is not the final definitive study to determine efficacy, a less stringent alpha of 0.10 may be justified for this Phase II proof-of-concept study which, if positive, would be followed by a confirmatory study [15]. While we expect most subjects to finish the study (based on the inclusion criteria), we have shown the impact on the power if approximately 20% of subjects do not finish the study. We have also varied the estimated proportion of patients failing to defecate by day 4 (i.e., not having a SBM) in the placebo group from 90% to 70% and in the prophylactic treated group from 40% to 50%.

For this Naloxogol randomized trial, we propose enrolling 36 subjects, 18 per group. The statistical power table below shows this sample size yields over 95% power using an alpha of 0.05 if the true day

Statistical Power of Log-Rank Test with n=18 subjects per group (36 total)

Complete study	ALPHA	Proportion Failing to Defecate at Day 4 (Placebo vs. Prophylactic Treated)				
		90% vs. 40%	90% vs. 50%	80% vs. 40%	80% vs. 50%	70% vs. 40%
100%	0.05	99.8%	98.4%	92.7%	76.0%	76.0%
	0.10	100.0%	99.4%	96.2%	84.9%	84.9%
80%	0.05	99.7%	97.6%	90.8%	72.5%	72.5%
	0.10	99.9%	99.0%	95.1%	82.2%	82.2%

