12.2.2 Determination of sample size

For the power analysis, the 4-day estimates of failure to defecate (i.e., failure to have a SBM) from the Kaplan-Meier plot presented in the Guardiola et. al. paper [4] was used as the estimate of lower GI tract paralysis. The figure below shows that the estimate of the percent of patients who failed to defecate (1 minus plotted proportion with defecation) by day 4 was 40% in the Prophylaxis group (i.e., the intervention group) vs. 90% in the non-prophylaxis (Treatment) group (i.e., the control group) (see yellow highlights in figure). We believe the 4-day estimate will be strongly related to the primary outcome of lower GI tract paralysis (≥ 3 days without a SBM).

90% (Placebo) vs. 40% (Prophylactic treatment), all subjects have complete follow-up, and the analysis is done using the log-rank test to compare survival curves. As sensitivity analysis, the table also shows the power of the study with this sample size under different scenarios. Because this is not the final definitive study to determine efficacy, a less stringent alpha of 0.10 may be justified for this Phase II proof-of-concept study which, if positive, would be followed by a confirmatory study [15]. While we expect most subjects to finish the study (based on the inclusion criteria), we have shown the impact on the power if approximately 20% of subjects do not finish the study. We have also varied the estimated proportion of patients failing to defecate by day 4 (i.e., not having a SBM) in the placebo group from 90% to 70% and in the prophylactic treated group from 40% to 50%.

Statistical Power of Log-Rank Test with n=18 subjects per group (36 total)

Complete study	ALPHA	Proportion Failing to Defecate at Day 4 (Placebo vs. Prophylactic Treated)				
		90% vs. 40%	90% vs. 50%	80% vs. 40%	80% vs. 50%	70% vs. 40%
100%	0.05	99.8%	98.4%	92.7%	76.0%	76.0%
	0.10	100.0%	99.4%	96.2%	84.9%	84.9%
80%	0.05	99.7%	97.6%	90.8%	72.5%	72.5%
	0.10	99.9%	99.0%	95.1%	82.2%	82.2%

For this Naloxogol randomized trial, we propose enrolling 36 subjects, 18 per group. The statistical power table below shows this sample size yields over 95% power using an alpha of 0.05 if the true day 4 estimated freedom of event (defecation) rates are

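### The power table in 12.2.2 implies about 10 days of observation that the design does not secure, so its powers for the smaller effects are overstated

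*Protocol*

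**What the plan says.** Protocol and SAP 12.2.2 set the sample size: "we propose enrolling 36 subjects, 18 per group". The inputs are the proportions still without an SBM at day 4 in a published comparison: "by day 4 was 40% in the Prophylaxis group" and "90% in the non-prophylaxis (Treatment) group". Power of over 95% is claimed at alpha 0.05 for 90% vs 40%, on condition that follow-up is complete. The length of that follow-up is not given.

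The table then varies the rates and adds rows for incomplete follow-up. The text says "we expect most subjects to finish the study (based on the inclusion criteria"), and of the 80% rows that "we have shown the impact on the power if approximately 20% of subjects do not finish the study".

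Other sections decide how long a patient is actually observed:

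- **Protocol 2.1** runs the primary window from randomization "to ICU discharge, death or 10 days of study drug administration (whichever comes first").
- **Protocol 4.1(c)** is the only inclusion criterion about stay: "Expected by the medical ICU attending physician to require admission to the MICU service for" at least 48 hours.
- **Protocol 5.6** removes a patient who has had no SBM at 6 days. Appendix 1 stops study drug at the same threshold but counts days from the start of scheduled opioids, which section 2.2 allows to be up to three days before randomization.

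**The concern.** Log-rank power depends on the number of events observed, and here the tabulated event is the first SBM. A table built on 10 days of risk time credits events that the trial will not see if patients leave the ICU on day 3, 4 or 5. Under 2.1 a patient discharged on day 3 has reached the end of the observation window and has in that sense finished, yet supplies 3 days of risk time. The 80% rows, offered as the less favourable case, do not cover this.

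The inclusion criteria cannot bear the weight put on them. An expected stay of 48 hours says nothing about remaining under observation for 10 days.

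The smaller-effect columns are the sensitivity analysis a reader would turn to if a 50-point difference proved optimistic. If they are too high, a null result would be read as coming from a better-powered comparison than the trial could provide. That matters for a pilot meant to inform the sample size of later trials.

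**Working it through.** **Inputs.** 18 per group; day-4 proportions without SBM of 90, 80 or 70% (placebo) and 40 or 50% (treated), from 12.2.2. Significance level from 12.2: "a two-sided p-value of ≤ 0.05 will be considered as statistically significant". Assumption: constant hazards, h = −ln(S4)/4, where S4 is the day-4 proportion without SBM.

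**Formula (Schoenfeld).** With T days of observation for everyone:

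- d = 18 × [(1 − S4,placebo^(T/4)) + (1 − S4,treated^(T/4))]
- HR = ln(S4,treated) / ln(S4,placebo)
- power = Φ(½ √d ln HR − 1.96)

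**Step 1: reproduce the 100% row with T = 10.**

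- 90/40: d = 18 × (0.232 + 0.899) = 20.35; ln HR = 2.163; Φ(4.88 − 1.96) = 99.8%.
- 80/50: d = 18 × (0.428 + 0.823) = 22.5; ln HR = 1.133; Φ(2.69 − 1.96) = 76.7%.
- 70/40: d = 18 × (0.590 + 0.899) = 26.8; ln HR = 0.944; Φ(2.44 − 1.96) = 68.5%.

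**Step 2: reproduce the 80% row** by adding exponential loss of 20% by day 10 (rate −ln(0.8)/10 = 0.0223 per day).

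| Alpha 0.05 | 90/40 | 90/50 | 80/40 | 80/50 | 70/40 |
|---|---|---|---|---|---|
| Printed, 100% | 99.8 | 98.4 | 92.7 | 76.0 | 76.0 |
| 10 days | 99.8 | 98.4 | 93.2 | 76.7 | 68.5 |
| Printed, 80% | 99.7 | 97.6 | 90.8 | 72.5 | 72.5 |
| 10 days, 20% loss | 99.7 | 97.6 | 91.2 | 73.1 | 65.1 |
| 4 days, no loss | 97.0 | 87.2 | 76.4 | 52.1 | 47.6 |

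Four columns match at 10 days in both rows; 4 days does not fit. Agreement with the 100% row within 2 points needs at least 4.5 days for 90/40, at least 7.2 for 90/50, 8.05 to 12.0 for 80/40 and 8.85 to 10.65 for 80/50. Only a horizon near 10 days fits all four. The 70/40 column does not fit even then, and it repeats 80/50 in every row.

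**Step 3: shorten the observation.** The Schoenfeld formula runs high here at short horizons, so these are simulated log-rank tests (at least 20,000 replicates, same hazards, two-sided 0.05). At 10 days the simulation gives about 99.8, 98, 93 and 76%, in line with the table.

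ICU stay is modelled as 2 days plus an exponential time, capped at 10 days. This is an assumption, since the documents give no length of stay. The 2-day minimum respects 4.1(c).

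| Observation | 90/40 | 90/50 | 80/40 | 80/50 |
|---|---|---|---|---|
| All capped at 6 days | 98 | 90 | 84 | 61–62 |
| Median stay 4 days | 93–94 | 81–82 | 73–74 | 50–51 |
| Median stay 5 days | 96 | 87 | 79 | 56–57 |
| Median stay 7 days | 98 | 91–92 | 84 | 63 |
| Median stay 10 days | 99 | 94 | 87 | 67–68 |
| Printed, 80% row | 99.7 | 97.6 | 90.8 | 72.5 |

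The 6-day cap needs no length of stay, but it assumes that removal under 5.6 ends observation and that the 6 days run from randomization. Counting from opioid start, as Appendix 1 does, would leave less time.

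Even with a median stay of 10 days only half the patients remain to day 10, by definition of the median; the 80% rows as reconstructed need about 80%.

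The alpha 0.10 rows behave alike: for 80/50, Schoenfeld gives 85.2% at 10 days (printed 84.9%) and 75.0% at 6 days.

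**The case against.** **The headline may be thought wrong.** A reader might infer that the design cannot deliver over 95% power. The documents do not support that. The claim is conditional on complete follow-up and applies to 90/40 only, where the effect is so large that 10 days are not needed: Schoenfeld gives 97.0% at 4 days, and simulation about 96% at a fixed 5 days or a median stay of 5 days. It falls below 95% only with shorter observation (about 93% at a fixed 4 days or a median of 4). With no stay given, failure cannot be asserted.

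**The effect may be thought to reach the primary outcome.** This is not shown. The table's event is first SBM; the primary event is at least 3 days without one, and many of those events would fall at about day 3. A rough simulation of the paralysis event (1,500 runs, exponential gaps between SBMs assumed) moved little with fixed follow-up of 10 versus 4 days: 84.6 versus 80.7% at 90/40, and 41.0 versus 38.7% at 80/50. The figures here concern first SBM only.

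**The 10-day horizon is inferred.** True. Section 12.2.2 does not state it, nor how the 20% loss was modelled. But one horizon and one loss model reproduce eight printed values within a point, and 10 days is the maximum named in 12.2.

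**The plan already shows a loss scenario.** Also true, so it would be wrong to say the whole table assumes that every patient stays 10 days. The loss allowed is modest and spread over 10 days, which is not the same as discharge within the first week.

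**Removal may not end observation.** Section 5.9 says outcomes such as ICU stay are still collected after study drug stops, so the 6-day figures are conditional. The stay-based figures do not depend on that rule.

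**Conclusion.** Wrong as written. Section 12.2.2 states no follow-up length, and four of its five columns fit only about 10 days of observation, which the discharge rule, the 48-hour criterion and the 6-day removal do not secure.

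The overstatement lies mainly in the smaller-effect columns. Against the 80% rows, and for assumed median stays of 4 to 10 days, 80/50 is lower by about 5 to 22 points and 90/50 by about 4 to 16. The 6-day cap costs about 11 points at 80/50 and 7 at 90/50.

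The over 95% figure at 90/40 is not secured rather than refuted; it depends on a median stay of about 5 days or more. The 70/40 column is a separate error (68.5% recomputed, 76.0% printed), probably a copy of 80/50.

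These sizes rest on constant hazards from the day-4 rates, first SBM as the event, and an assumed stay distribution.

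**What to change.** In 12.2.2 of both the protocol and the SAP:

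1. State the follow-up horizon and the event behind the table.
2. Recompute every row, correcting the 70/40 column, with observation ending at ICU discharge, death, removal or day 10. Use the unit's own distribution of ICU stay after randomization, or a shown range such as medians of 4, 5, 7 and 10 days.
3. Replace the printed 100% and 80% figures with these, and state the stay on which the over 95% claim depends.
4. Delete the parenthetical that rests near-complete follow-up on the inclusion criteria.
5. Say whether removal at 6 days ends observation of SBMs, and reconcile the day count in 5.6 with the one in Appendix 1, so that the calculation has a defined censoring rule.

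N stays at 36. The cost is a recalculation and a wording change; the downside is that the stated powers become less favourable.

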12.3 Data monitoring committee

A Data and Safety Monitoring Board (DSMB) will be formed for this study. The DSMB will consist of an intensivist, gastroenterologist and a pharmacist who have experience in the management of

Drug Substance: Movantik
Study Number: ESR-15-11000
Tufts IRB #12043
Version: Protocol version #19
Date: September 10, 2018

gastrointestinal-related conditions in the critically ill. The study biostatistician, [name], will also be a part of the DSMB in a consultative role. The DSMB will review all subject data (in a blinded fashion) after the enrollment of the first 10 subjects in the study and then after the enrollment of the first 20 subjects. Any unanticipated SAE will also automatically trigger a DSMB review. The DSMB will meet at least once every 6 months in the event that the pace of study enrollment does not trigger a DSMB meeting in a particular 6 month period. DSMB members will not be associated with the study. The study biostatistician will remain blinded until the final results of the study are analyzed. If the DSMB requires the A group and B group coding, then the research pharmacist will send a confidential email to the DSMB that contains the A and B assignments. The charter for the DSMB is listed under Appendix 9.

Appendix 1. Study Laxative Guideline

No spontaneous bowel movement in ≥ 3 days⁴?

Step 1: Initiate: Senna one tablet (8.6 mg) PO/NG daily AND polyethylene glycol 3350 17 g PO/NG daily. If SBM occurs then stop step 1 therapy but keep patient on docusate.

No spontaneous bowel movement in ≥ 4 days⁴?

Step 2: Increase Senna to 2 tablets (17.2 mg) PO/NG daily AND polyethylene glycol 3350 to 34 g PO/NG daily and insert a bisacodyl suppository 10mg PR x 1. If bowel movement occurs then stop all laxative study protocol therapy but keep patient on docusate.

No spontaneous bowel movement in ≥ 5 days⁴?

Step 3: Repeat Step 2 AND if no spontaneous bowel movement within 2 hours of administering the bisacodyl suppository, administer a 10oz bottle of magnesium citrate sodium phosphate. If bowel movement occurs then stop all study laxative protocol but keep patient on docusate.

No spontaneous bowel movement in ≥ 6 days⁴?

Step 4: Discontinue study medication (but do not unblind patient assignment). Repeat Step 3, initiate methylnaltrexone (Relistor) sc x once and consider a consultation to gastroenterology or surgery. [Note: If patient weight is 38-62 kg then methylnaltrexone dose = 8mg; if patient weight is 62-144 kg then methylnaltrexone dose = 12mg].

[figure not shown]
⁴From the day of initiation of scheduled opioid therapy (ie. IV fentanyl ≥ 100 mcg/day or equivalent)

Drug Substance: Movantik
 Study Number: ESR-15-11000
 Tufts IRB #12043
 Version: Protocol version #19
 Date: September 10, 2018

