5.6 Concomitant and post-study treatment

All patients enrolled in the study will be initiated on the following:

1. Docusate 100mg twice daily administered orally (or enterally).

AND

2. Study Laxative Guideline (see Appendix 1)

Drug Substance: Movantik
Study Number: ESR-15-11000
Tufts IRB #12043
Version: Protocol version #19
Date: September 10, 2018

A standard laxative guideline does not currently exist in any ICUs at Tufts Medical Center. Therefore in an effort to standardize the administration of laxatives in the study, the investigative team developed a study laxative guideline that is similar to current laxative prescribing practices in the medical ICU at Tufts MC for patients that do not have spontaneous bowel movement for ≥ 3 days. Realizing the importance of having a formal, tiered laxative guideline that mimics that which is used in routine practice for medical ICU patients at Tufts Medical Center, the investigators basically formalized the approaches that are most commonly used in practice to develop (what is felt) to be a reasonably aggressive guideline. It should be noted that if study patient fails to have spontaneous bowel movement at 6 days (despite ever more intensive laxative treatment steps occurring), the patient will be removed from the study and the clinical ICU team will have the option of administering SC methylnaltrexone or intervening in whatever way these see fit to treat the constipation. Of course, prior to study day #6, if the medical ICU team feels that a subject's constipation is severe enough to warrant study removal (and perhaps methylnaltrexone administration) then the subject would be removed from the study earlier. It will be communicated to each subject's ICU physician that the study laxative guideline does not have to be rigidly followed if the subject's physician deems that a deviation from the guideline is required based on their clinical evaluation of the subject.

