5.8 Discontinuation of investigational product

5.8.1. Procedures for discontinuation of a subject from investigational product

Study drug administration will be stopped when one of the following occurs:

1. The subject experiences an adverse event potentially attributable to the study drug that is deemed, in the opinion of principal investigator, to warrant discontinuation of therapy.
2. The patient requires use of the Level 4 Study Laxative Guideline (i.e., methylnaltrexone)
3. Scheduled opioid therapy is stopped for ≥ 24 hours and the patient has had ≥ 1 SBM since the time of study enrollment.
4. The patient has been administered 10 days of study medication.
5. The patient is discharged from the ICU.
6. The patient dies in the ICU.
7. The patient requires a strong CYP3A4 inhibitor medication (and no other therapeutic alternative medication without this property can be used)
8. The patient develops excessive diarrhea defined as ≥ 3 SBMs with a Bliss Score of 3 or 4 in a 24 hour period. When excessive diarrhea first occurs, study medication will be held. In addition, all laxatives

Drug Substance: Movantik
 Study Number: ESR-15-11000
 Tufts IRB #12043
 Version: Protocol version #19
 Date: September 10, 2018

will be stopped (including docusate) and the investigative team will work with the subject's clinical team to identify other possible causes for the excessive diarrhea (e.g. enteral nutrition formulation choice, C. difficile infection etc). In a further 24 hours (48 hours after the last study medication dose), if excessive diarrhea persists, the study medication will be permanently discontinued. However, if the subject no longer has excessive diarrhea in a further 24 hours (48 hours after the last study medication dose), study medication will be resumed at the original dose. If excessive diarrhea occurs again after study medication is resumed, then the study medication will be permanently stopped.

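### For a patient who responds to the suppository, the laxative guideline's stop rules and escalation rules conflict, and nothing says which governs or whether the day count restarts

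*Protocol*

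**What the plan says.** Protocol 2.1 Note 1 counts any rectal output as an SBM "as long as it is not temporally related to the insertion of a rectal tube or the insertion of a suppository", and refers to Appendix 1. Neither place gives a number of hours.

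Appendix 1 is a four-step ladder. Its footnote counts days from the start of scheduled opioid therapy. Step 1 (day 3) stops on an SBM. Step 2 (day 4) introduces the bisacodyl suppository, and its stop rule changes to: "If bowel movement occurs then stop all laxative study protocol therapy but keep patient on docusate". Step 3 (day 5) repeats Step 2 and adds magnesium citrate "if no spontaneous bowel movement within 2 hours of administering the bisacodyl suppository". The next sentence reads: "If bowel movement occurs then stop all study laxative protocol but keep patient on docusate". Step 4 (day 6) stops study drug, repeats Step 3 and gives methylnaltrexone. The entry question for every step asks about spontaneous movements.

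Section 5.6 removes a patient from the study "if study patient fails to have spontaneous bowel movement at 6 days". It also tells physicians that "the study laxative guideline does not have to be rigidly followed" when their clinical evaluation calls for a deviation. Section 5.8.1 item 2 stops study drug when the methylnaltrexone level is needed. Item 3 stops it when: "Scheduled opioid therapy is stopped for ≥ 24 hours and the patient has had ≥ 1 SBM since the time of study enrollment".

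**The concern.** Output within 2 hours of a suppository is the plainest example of what Note 1 excludes. Step 3 therefore asks for something that the definition normally rules out, and a patient in whom the suppository worked still satisfies the condition for magnesium citrate. The following sentence tells staff to stop. The same clash recurs the next day: an induced movement has met the stop rule, but the SBM-free count from opioid start keeps running toward Step 4 and removal.

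On the literal path, a patient who has just passed stool receives more laxative and loses study drug. Section 1.4 item i expects that no patient will get more laxative than is clinically needed. Different nurses and physicians could follow different rules in good faith. That would affect laxative use, study drug exposure, days without a SBM and time to first SBM.

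**Working it through.** No figure in the plan rests on this point, so there is none to reproduce. The check compares the rules and then works out the timing.

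**Rules as they apply to a patient whose only output followed the suppository**

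| Rule | Acts on | Result |
|---|---|---|
| Step 2 stop rule | any bowel movement | stop study laxatives |
| Step 3 entry, day 5 | SBM | enter Step 3 |
| Step 3 magnesium citrate trigger | SBM within 2 hours | give it |
| Step 3 stop rule | any bowel movement | stop study laxatives |
| Step 4 entry, day 6 | SBM | stop study drug, give methylnaltrexone |
| 5.6 removal, day 6 | SBM | remove from study |

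Two rows say stop and four say escalate. No text ranks them, and none says whether an induced movement restarts the count.

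**Added treatment on the literal path** (a Step 2 responder whose later output is all classed as induced)
- Suppositories at Steps 2, 3 and 4: 3 in total, so 3 − 1 = 2 beyond the one that worked.
- Magnesium citrate at Step 3 and again at Step 4: up to 2 bottles.
- Methylnaltrexone: 1 dose.
- Under the stop-rule reading, all of these are 0.

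**Timing.** Let L be the days from opioid start to randomization, with no SBM in that time. The 2.2 note and exclusion o allow at most 3 days. Steps 2, 3 and 4 fall on post-randomization days 4 − L, 5 − L and 6 − L. Under section 12.2 the earliest primary event is on day 3. Study drug days forgone at Step 4 are at most 10 − (6 − L).

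| L | Step 2 | Step 3 | Step 4 | Days forgone, at most |
|---|---|---|---|---|
| 0 | 4 | 5 | 6 | 10 − 6 = 4 |
| 1 | 3 | 4 | 5 | 10 − 5 = 5 |
| 2 | 2 | 3 | 4 | 10 − 4 = 6 |

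Step 4 needs 6 SBM-free days counted from opioid start. At most 3 of these can precede randomization, so at least 3 follow it and the first primary event has already occurred. Step 3 falls on day 3 or later for L up to 2. Between 2 and 3 days it would fall just before day 3. Such a patient is close to the 3 SBM-free days that would be preexisting paralysis under 2.1 Note 2, and the documents give no numbers for this group. Nothing is claimed for it.

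**The missing window** is a smaller, separate matter. At L = 1 the Step 2 suppository and the earliest primary event share day 3. At L = 2 the suppository falls on day 2, before the event, so how its output is classed could decide whether the event occurs. One reclassified event moves an arm's incidence by 1/18 = 5.6 points. The window also affects 5.8.1 item 3, because a patient off opioids whose only output was induced has not met its SBM requirement.

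**The case against.** The best defence is that the stop rules show what was meant. Step 1 stops on an SBM. At Step 2, where the suppository enters, the wording becomes any bowel movement and ends all study laxatives. That change fits an intention that induced output should end the ladder. To reach methylnaltrexone, staff would have to pass over that rule repeatedly, although the investigative team is in the ICU each morning (5.7) and the physician may deviate (5.6). It is also a plain reading, not a stated rule, that output within 2 hours is temporally related.

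Much of this stands. A reader might infer that responders will be escalated and removed. The documents do not support that: escalation is one literal reading, and the stop rules and the override point the other way. A reader might also infer a biased primary comparison. That is not supported either, because Step 4 cannot precede the first primary event and the documents do not say how many patients respond to a suppository. Nor is suppository output left unclassified: Note 1 classifies it and lacks only the hours.

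The defence does not supply a governing rule. The Step 3 and 4 entry questions and the 5.6 removal rule keep the word *spontaneous*, the count runs from opioid start, and nothing says that an induced movement resets it. The override lets a physician depart from the guideline but does not say what the guideline requires.

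**Conclusion.** This is an internal inconsistency in a treatment rule, minor to should-fix. A suppository responder meets both the rule to stop laxatives and the rules that lead to more laxative, loss of study drug and removal.

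The added treatment and the 4 to 6 forgone study drug days shown above are upper limits. They assume that all later output is classed as induced, that staff follow the SBM-worded rules, and that the patient would otherwise have completed 10 days of study drug. The consequences fall on treatment exposure and secondary outcomes. The undefined window is mainly missing detail, with a limited route to the primary event. No shift in the treatment difference is claimed.

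**What to change.** 1. In Appendix 1 Step 3, change the magnesium citrate condition to *no bowel movement of any kind within 2 hours*.
2. In Appendix 1 and 5.6, state that any bowel movement after Step 2 or 3 meets the stop rule and restarts, from that movement, the day count for Steps 1 to 4 and for the 6-day removal rule. Leave physician override unchanged. State that only SBMs as defined in 2.1 Note 1 count for outcomes.
3. As a minor addition, state before unblinding how many hours after a suppository count as temporally related. Record suppository time and all rectal output, marked induced or spontaneous, on the daily forms. At present the Appendix 9 table is headed for spontaneous movements only. Appendix 10 lists laxatives by shift with no suppository time, although it asks for the time of a new rectal tube.

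The cost is a few text edits and form fields, with no extra patients, visits or procedures. The downside is that a responder who then stops passing stool reaches methylnaltrexone later unless the physician intervenes. After a movement on opioid day 4, Step 4 would fall on day 4 + 6 = 10 instead of day 6. Because Note 1 sets no minimum size, a trivial output would also restart the count, and physician override is the safeguard there.
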